## 8 Design of the Clinical Investigation

### 8.1 General

The test will be a two group prospective cross-over design, within subject comparison. Amputees are a small proportion of the general population. The population group specified in the inclusion/exclusion criteria is a further subsample of amputees. For practical reasons, i.e. to achieve statistical power, it is therefore more feasible to use within-subject comparison rather than creating study arms to compare. Furthermore, as mobile amputees generally have and use a prosthetic device for their daily activities, within-comparison is feasible comparing to the subject's previous device.

All investigational activities will be conducted at MCOP Silver Spring Prosthetic Clinic ([name]), Medical Center Boston, MA Prosthetic Clinic ([name]) and Motus Research ([name]).

As stated above the primary endpoint is the perceived exertion during walking measured by the Borg scale before and after 6MWT, see table 4, and the secondary endpoints are focused on the general mobility performance and efficacy of the investigational device, as well as performance of gait functions and ease of set up for average to highly active transfemoral/knee disarticulation amputees and CPOs. See previous chapter on objectives and hypothesis and Table 4 for rationale.

Drop-outs and withdrawals may be replaced if deemed necessary to fulfil the methodological standards of the study.

#### Instruments for data collection will include the following:

The Six Minute Walk test (6MWT) is simply a record of the distance traveled by a given patient at his or her self-selected walking speed over a period of six minutes. All that is required is a stopwatch and a walking corridor or track of known distance.

The Borg Scale of Perceived Exertion is a subjective rating scale on which people indicate their perceived exertion and has been used with people with lower-limb amputation.

The Amputee mobility predictor (AMPro) is a 20-item scale that was originally developed to provide a more objective approach to the assignment of Medicare K-levels. The scale includes tasks intended to assess sitting balance, transfers, standing balance, gait, and obstacle negotiation and takes around 15 minutes to administer.

The Prosthetic Mobility questionnaire (PMQ) is a measure of perceived ability to perform a range of ambulation and transfer tasks with a lower limb prosthesis. PMQ has been reported to have high internal consistency, great test-retest reliability, and good convergent construct validity in people with lower limb amputation. PMQ will be administered as recommended by Franchignoni et al. PMQ is scored from 0 to 4; higher scores indicate higher perceived ability.

The Prosthesis Evaluation Questionnaire (PEQ) measures prosthetic-related quality of life. It consists of 82 items grouped into nine subscales. In addition, there are individual questions not contained in the subscales regarding satisfaction, pain, transfers, prosthetic care, self-efficacy, and importance.

L-test of functional mobility is a modified version of the Timed up and go test (TUG) developed for more active lower limb amputees. The patient begins the test seated in a chair, ideally positioned in an exam room and facing the entrance to the hallway. The patient rises from the chair, walks three meters into the hallway, turns 90 degrees and then walks an additional seven meters down the hallway. Upon completing seven meters, he turns 180 degrees, returns down the hallway, turns 90 degrees to face the exam room, and returns the three meters to his chair, where he retakes his seat.

The Plus-M is a self-report instrument for measuring mobility of adults (age 18+) with lower limb amputation who have experience of using a prosthesis. PLUS-M measures prosthetic users' mobility (i.e., their ability to move intentionally and independently from one place to another). The questions assess respondents' perceived ability to carry out specific activities that require use of both limbs. PLUS-M questions cover movements that range from basic ambulation such as walking a short distance indoors to more complex outdoor activities such as hiking for long distances.

### Video

#### Data logging by Össur Logic

See chapter **10.2 Sample size calculation** and **Table 4** for analysis of variables.

#### **Equipment required for each amputee subject:**

- Pen/pencil
- Detailed protocol
- Printed out instruments and instructions (Case report forms, PEQ, PMQ, AMPro, PLUS-M, Borg scale, in-house questionnaire)
- Logbook/Notebook
- Stopwatch/phone for 6MWT
- Markers and a measured corridor/course of known distance for 6MWT and L-test
- Chair for L-test and AMPro
- Measuring tape
- 10cm obstacle for AMPro
- Investigational device: Power Knee Mainstream (along with test foot and components as applicable).
- Tools for fitting

The equipment used does not require specific monitoring, maintenance or calibration procedures.

## **8.2 Investigational Device(s) and Comparator(s)**

The investigational device is a powered microprocessor controlled prosthetic knee, with the same intended use as the previous version of the device (POWER KNEE II, a CE- marked device). See full details on the investigational device in **Clinical investigators brochure [3]**.

When the investigational device is on the market the device will be a single user device, with a typical use time of 5 years. Due to supply shortage, for clinical testing purposes the same investigational device may be used iteratively for periods of up to 3 weeks, maximum 3 times. Before refitting of a device, a reset to manufacturer settings will be performed as well as inspection for damage or malfunction. This supply shortage only refers to

visits 1 and 2 in the test procedure due to time limitations. For visit 3, investigational devices will be available for all users.

The subjects will be asked to use the investigational device as their primary prosthesis for **2-3** weeks. Individual exposure will differ between subjects. Subjects are expected to use the investigational device for their daily living activities as they would with any other prosthesis, for up to 18 hours a day depending on the individual. The comparator device will not be used within the timeframe of the intervention period of the study. Subjects will evaluate and provide feedback on their exposure of the comparator at baseline and prior to them being fitted to the investigational device or after, depending on the group they are assigned to. The investigational device is used with a smart app to adjust and interact with the knee. Össur Logic is an iOS smart app and it is required to adjust and interact with the knee. It is a standalone software as a medical device, used with other bionic devices as well, the app is documented separately, see **[1]**.

The comparator device is the users current prosthesis, it may be any passive MPK or a previous version of the Power Knee (AMPK), depending on the subject. Both have the same intended use and population as the investigational device.

The subject will be using the remaining part of their current prosthetic system with the investigational device, as it was used with the comparator device. If this is not possible, an advanced ESAR foot will be used and provided by Össur.

No other device, medication or intervention will be used. Aside from the Össur Logic app which is used to interact with the knee.

**15-18** subjects are to be enrolled and therefore **15-18** investigational devices will be used, as the devices are intended to be used by a single patient; one for each subject.

## 8.3 Subjects

All subjects will be dispositioned as follows:

- Screen Failure: Subject did not pass screening procedures, not called in for clinical visit;
- Candidate for enrollment: Passed screening procedures, accepts to come in for clinical visit;
- Enrolled: Subject signs informed consent;
- Fitted: Subject leaves the clinic on the investigational device;
- Discontinued: Candidate for enrollment or Enrolled subject whose participation ended because they withdrew consent, were withdrawn by the Investigator, were lost to follow up, or died;]

Table 5 Inclusion/Exclusion criteria

Inclusion:	Exclusion:
Only patients with the following characteristics are eligible for study entry:	Patients with the following characteristics are not eligible for study entry:
50Kg < body weight < 116Kg	50Kg > body weight > 116Kg
K3-K4 amputees with unilateral transfemoral amputation or knee disarticulation	Bilateral amputees
Allows for 37mm knee center height to dome of pyramid alignment	Users with socket problems
Currently using a MPK or Power Knee	Users with co-morbidities in the contra-lateral limb, which affect their functional mobility
Older than 18 years old	Younger than 18 years old
No socket issues/changes in the last 6 weeks and no socket changes expected during the duration of the study period.	Users with stump pain
Comfortable and stable socket fit	Users with cognitive impairment
Willing and able to participate in the study and follow the protocol	Users involved in other clinical tests and/or receiving treatment that the testing might affect.

A subject can withdraw from participation at any time, at his/her discretion, and this will not have any consequences for the participant's treatment. In such cases a report stating reasons for discontinuation of the participant shall be prepared by the PI, if the participant wants to disclose those reasons. No further investigational procedures concerning the subject will be conducted, except for a statement explaining the reason for withdrawal (if disclosed), including but not limited to: interacting or interviewing the subject in order to obtain data on him/her; obtaining additional private information on the subject by either observing the subject or collecting or receiving such information from any source.

The LPI can withdraw the participant from the trial at any time. The reasons shall be documented. There are no pre-specified criteria for discontinuation of participants from the trial. The discontinuation of participants in the trial will not result in replacement with new participants. If withdrawal is due to problems related to the investigational device the participant will be asked for permission to follow the status/condition outside the clinical investigation. The follow-up will be individualized.

Subjects will be enrolled at the clinic, the investigational site that they were contacted from.

The total time period required to implement the clinical investigation is expected to be 15-20 weeks. Each individual subject is expected to participate in the clinical investigation for 4-15 weeks. The estimated time needed to include this number (enrolment period) is up to 6 weeks.

At least 15 subjects are required to finish the protocol (3 visits) for statistical data analysis, as specified in chapter 10.2 Sample size calculation.

## 8.4 Procedures

### i) Recruitment

Potential subjects will be identified from the customer base of the Local Principal Investigator (LPI). The LPI evaluates, based on previous experience of interaction with and servicing of patients, if a potential participant is cognitively capable. If a potential participant fits the inclusion and exclusion criteria the PI will contact them via telephone. During the telephone call the LPI will verify if they are interested in participating in a study. If interest is expressed at this point they will answer some screening questions and questions relating to the duration of the study, number of clinical visits required, and the investigational device will be answered and if the eligibility criteria are met they will be invited for the 1st visit.

### ii) Test procedure

There are **three** scheduled and **one** optional study event, all testing procedures will be conducted at the study site. At the initial visit, the first study event, for each subject a researcher qualified to obtain informed consent will seat the subject and proceed as described in chapter **13.8 Informed consent**.

Procedure for resetting and inspection of investigational devices between users:

In Ossur Logic App, default parameters of the knee will be restored using the default profile.

An activity report is generated in order to record the number of steps performed on the device before the next user starts using the device.

Visual inspection of the device condition performed to identify any signs of wear or damaged parts. If damaged parts or sign of wear are observed, the knee shall be segregated and not fitted to a new user.

Following the instructions provided in the Instruction for Use, the knee exterior surface and the battery pack complete outer surfaces will be cleaned.

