### Co-Investigator

- Collect Data
- Analyze results
- Write report
- Assist in conduct of trial procedures at investigators' site
- Assist in fitting users with trial device (and back to their prescribed prosthesis, if applicable)
- Perform reset and inspection of investigational devices between users (engineer).

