### 13.2 Device related risk

Each device designed and manufactured by Össur is subjected to thorough risk assessment, analysis and control, with failure mode effect analysis and hazard analysis, according to QM1673 Risk Management process, based on ISO 14971 (Risk Management for Medical Devices). All changes performed to the software and/or functions of a device are submitted to multi-level verification and, as applicable, validation processes before being authorized for use in a clinical investigation.

The FMEA and hazard analysis are tools for identifying harms, the sequence of events, their probability, and the potential failures that can cause these harms. Anticipated adverse device effects and residual risks associated with the investigational device, are identified in the **Hazard Analysis Documentation [3]** and **Chapter 7 in the Clinical Investigator's Brochure [4]**.

The Hazard analysis document [3] contains analysis on foreseeable adverse events and anticipated adverse device effects, together with their likely incidence, mitigation or treatment.

Reasonably foreseeable misuses:

- Use of product by user exceeding the maximum user weight.
- Use of the product by user exceeding the activity or impact levels specified above.
- Use of the product for sport activities.
- Submersion of the product in water or exposure to quantity of water exceeding what is considered normal weather.
- Failure to properly maintain the product and/or maintain the product to the expected level of cleanliness.
- Product contamination by foreign substances or operation of the product in dirty or dusty environments.
- Failure to follow recommended or mandatory service schedule.
- Use of the product over the specified maximum life duration.

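### Section 8.2 requires a malfunction inspection before a shared knee is refitted, but the 8.4 ii hand-over steps inspect only by eye and withhold a knee only for visible damage or wear

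*Combined protocol and SAP*

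**What the plan says.** Section 8.2 explains that, because of a supply shortage, "the same investigational device may be used iteratively for periods of up to 3 weeks, maximum 3 times". It limits the shortage to visits 1 and 2 and expects enough devices for everyone at visit 3. It sets a condition on sharing: "Before refitting of a device, a reset to manufacturer settings will be performed as well as inspection for damage or malfunction". The same section also describes 15 to 18 devices for 15 to 18 subjects, "as the devices are intended to be used by a single patient; one for each subject", so how many knees will really be shared is left open.

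The working procedure is in 8.4 ii, under a heading for resetting and inspecting devices between users. It has four steps:
- default parameters are restored in the app;
- "An activity report is generated in order to record the number of steps performed on the device";
- "Visual inspection of the device condition performed to identify any signs of wear or damaged parts";
- the outer surfaces of the knee and battery pack are cleaned.

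The rule for withholding a knee is "If damaged parts or sign of wear are observed, the knee shall be segregated and not fitted to a new user". Section 8.6 gives the reset and inspection to an engineer among the co-investigators, without adding test steps.

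Section 13.2 lists foreseeable misuses. They include "Submersion of the product in water or exposure to quantity of water exceeding what is considered normal weather", dirty or dusty use, and sport.

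**The concern.** The safeguard stated in 8.2 has two parts, damage and malfunction. The procedure written to carry it out covers only the first. A person following 8.4 ii to the letter could complete every step and pass on a knee whose motor, stance support or battery connection is faulty, provided that nothing shows on the outside. No step asks the returning subject whether the knee misbehaved, was submerged or took an impact, and no action is tied to the step count.

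The person exposed is the next wearer. The knee is motorised, battery-powered and pre-market, and section 6 states that no clinical data exist for it. Section 8.2 describes a single-user product once marketed, so the sharing is created by the study, and the hand-over inspection is the control specific to it.

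**Working it through.** The plan gives no figure for this point, so the check is a comparison of texts followed by simple counts.

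**Requirement against procedure**
- Damage: required by 8.2; covered in 8.4 ii by the visual inspection and the segregation rule.
- Malfunction: required by 8.2; no step in 8.4 ii is directed at it. The reset and activity report use the app, so they could expose a gross power or connection fault, but they are not described as a functional check and no pass or fail follows from them.
- Withholding: 8.4 ii acts on observed damage or wear only. It does not mention a malfunction, whether found or reported.

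**What else would catch a fault**
- At visit 2 the Group 1 subject does the 6MWT and L-test on the knee just before giving it back (8.4, Visit 2). As described in 8.1, these cover level walking, turns and rising from and returning to a chair, but not stairs or ramps.
- The next subject is fitted and trained on varied terrain (8.4, Visit 1), but by then that person is wearing the knee.
- Section 9 has the device form log the return of malfunctioning devices, and 14.2 has device deficiencies recorded. Neither is linked to the 8.4 ii withholding rule.
- A subject who withdraws while wearing the knee may return it without the visit tests, because 8.3 stops further investigational procedures for that subject. Section 8.3 also foresees withdrawal because of device problems.

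**Number of hand-overs of a used knee (N = 15 to 18)**
- One knee per subject: 0.
- Group 1 starts together and each of its knees passes once to Group 2: the count is the smaller group. N = 15 split 8/7 gives 7; N = 18 split 9/9 gives 9.
- Every knee used three times, with staggered enrolment: N − N/3. For N = 15, 15 − 5 = 10; for N = 18, 18 − 6 = 12. This is a ceiling, since it needs full sharing across sites.

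**Prior wear at the 8.2 upper limit of 18 hours a day**
- Second user: 3 weeks × 7 days × 18 h = 378 h.
- Third user: 6 weeks × 7 days × 18 h = 756 h.
- For scale, six weeks is 6/(5 × 52) = 2.3% of the 5-year typical use time in 8.2. Ordinary wear is thus a small part of the concern; an unseen fault or event is the larger part.

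**The case against.** The strongest reply is that the requirement already exists. Section 8.2 makes the malfunction inspection a condition of refitting, 8.6 assigns an engineer, and nothing in 8.4 ii cancels either. On that view only work-instruction detail is missing. Part of this stands: a reader might infer that the plan has no safeguard against malfunction, or that the next wearer is bound to be the first to test a returned knee. The documents support neither, given 8.2, the visit 2 tests, the device form in section 9 and the deficiency recording in 14.2. What does not stand is that the gap is only one of detail. The operative withholding rule is narrower than the stated safeguard, and it is the rule that staff will follow.

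A second reply is that a brief functional check adds little for a knee that has just been through the 6MWT and L-test. That is largely right. The gain lies mainly with knees returned without those tests, and with events the subject can report.

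A third is that a withdrawn subject can still disclose a reason, that the local investigator documents reasons when withdrawing someone, and that 8.3 does not clearly forbid a question about the device. This is fair, and it is why the question should be put where the subject is available.

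A reader might also take 18 − 15 = 3 as the most knees that could come back untested. It is a recruitment margin, not a bound; nothing in the plan caps withdrawals. Nor does the misuse list in 13.2 justify holding a knee after any sport or dust exposure. Users are K3 to K4, outdoor use is intended, and such holds could be frequent during a shortage.

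Finally, the hazard analysis, brochure and Instructions for Use were not available and may contain a suitable check. Section 8.4 ii cites the Instructions for Use only for cleaning.

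**Conclusion.** The point holds as a minor one. The steps and withholding rule in 8.4 ii do not deliver the malfunction inspection that 8.2 requires. The affected person is the next wearer of a knee that is actually shared. That means 0 hand-overs if each subject has a separate device, about 7 to 9 if Group 1 knees pass to Group 2, and a ceiling of 10 to 12, within a shortage that 8.2 limits to visits 1 and 2. It matters most for a knee returned without the visit tests.

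The counts assume 15 to 18 subjects, near-equal groups and the three-use limit. The documents give no rate of latent fault or misuse, so no probability of harm is stated. A reader might infer that reuse biases the comparison or weakens power; nothing in the documents shows that, and it is not part of this point.

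**What to change.** Amend 8.4 ii as follows.
1. Before any refitting, the engineer named in 8.6 does a brief functional check with the knee off the patient: powered flexion and extension, support under load, battery contacts, and any device faults shown in the app. Pass or fail is recorded on the Investigational Device Management Form.
2. The returning subject, if available, is asked about malfunction, submersion or excess water, heavy contamination, and falls or impacts on the knee. A 'yes' directs the engineer to the part concerned.
3. The segregation rule is widened. Besides visible damage or wear, it covers a failed functional check, and a reported malfunction or submersion that the engineer has not cleared. Sport or dust exposure alone need not hold a knee.

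If the hazard analysis or Instructions for Use already contain such a check, 8.4 ii should cite it and still widen the segregation rule.

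The cost is a few lines of text, an entry on the device form and a few minutes at each of at most 12 hand-overs. A knee that needs a closer look takes longer and may delay a fitting while supply is short. Visits, endpoints and the analysis do not change.

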#### Visit 1:

The subject will be consented and enrolled after verification of the inclusion/exclusion criteria. Potential risk of participating in the investigation will be explained to the subject.

The LPI will communicate to the study monitor the number of users he has identified that meet the inclusion criteria and are willing to participate.

Subjects will be randomized into 2 groups, using a random number generator. Half of the subjects (Group 1) will then be fitted with the investigational device. Prior to fitting the subjects of Group 1 will be asked to provide feedback on the current prosthesis, by filling in a set of questionnaires **and performing the AMPro, L-test and 6MWT with Borg scale**, to obtain baseline data. Subjects may be videotaped during fitting and while performing functional tests, care will be taken to blur out faces and other personally identifiable markers such as tattoos and birthmarks.

Users will be fitted within the standard methods of prosthetic fitting, alignment, introduction, training and walking on various terrain. After being fitted with the investigational device subjects will receive functional training on the investigational device prior to going home and using it as their usual prosthesis for approximately 2-3 weeks. They will be given an appointment for the follow up visit prior to leaving the testing site.

The other half (Group 2) will stay on their prescribed prosthesis until the next visit in 2-3 weeks.

CPO subjects will provide feedback on the ease of setup and fitting, they will also be videotaped during setup. Care will be taken to blur out faces and other personally identifiable markers such as tattoos and birthmarks.

